#### *Severity of Adverse Events*

The severity of all AEs will be assessed by the study clinician based on the following guidelines.

- **Mild**—Events require minimal or no treatment and do not interfere with the participant's daily activities.

- **Moderate**—Events result in a low level of inconvenience or concern. Moderate events may cause some interference with functioning and may require therapeutic measures.
- **Severe**—Events that prevent a participant’s usual daily activity and require systemic drug therapy or other treatment. Of note, the term “severe” does not necessarily equate to “serious.”
- **Potentially Life-Threatening**—Events that require emergency room visit or hospitalization. Potentially life-threatening symptoms causing incapacitation with intervention needed to prevent disability or death.

A toxicity table for solicited AEs with guides for assessing severity of the specific event is found in Appendix 8.

#### *Causality of Adverse Event*

The study investigator/s will determine the causal relationship between the study product and the AE. The causality assessment is made on the basis of the available information at the time of reporting and can be subsequently changed according to follow-up information. Determining of causality is based on clinical judgment and should take into considerations the following factors:

- Is there a temporal (time-based) relationship between the event and administration of the study product?
- Is there a plausible biological mechanism for the study product to cause the AE?
- Is there a possible alternative etiology for the AE such as concurrent illness or concomitant medications?
- Are there previous reports of similar AEs associated with the study product?

For this study, the investigator/s must classify the causality of the AE according to the categories defined below:

**Related:** There is a reasonable possibility that the product caused the event. “Reasonable possibility” means that there is evidence to suggest a causal relationship between the study product and the AE.

**Not Related:** There is not a reasonable possibility that the administration of the study product caused the event.

#### *Follow-up of Adverse Event*

All reported AEs should be followed until resolution or stabilization, or until the participant’s participation in the study ends. Participants who have an ongoing study product–related SAEs at study completion or at discontinuation from the study will be followed by the PI or his designee until the event is resolved or determined to be irreversible, chronic, or stable by the PI.

The outcome of an adverse event will be assessed as at the time of last observation as per the following categories:

- Recovered/resolved without sequelae.
- Recovered/resolved with sequelae.
- Ongoing at the end of the study.
- Death.
- Unknown. The outcome of the AE is not known.

#### *Reporting of SAEs and SUSARs*

## STUDY PEDIATRICIAN REPORTING TO INVESTIGATORS

Within 24 hours of the study pediatrician's awareness of an SAE as defined in the protocol, an AE/SAE form must be completed and submitted to the study's PIs by email. The ISM will also be notified.

The initial AE/SAE form should be completed with all information known at the time and should include as much as possible the following:

- Name and contact of the investigator submitting the AE/SAE report.
- Participant ID number.
- Participant age.
- Date participant received study drug, including cohort group.
- Description of the serious adverse event.
- Date of event onset and date of event resolution.
- Investigator's assessment of severity, causality, and expectedness.
- Action taken and current status.
- If available, any diagnostic test reports or hospital records that may help the sponsor to evaluate the SAE.

The site PI will be responsible for notifying the Maseno University Ethics and Research Committee and the PPB, and the PI will be responsible for notifying the PATH research ethics committee (REC) as per the respective ethical or regulatory authority's reporting requirements.

### *Notification and Review of SAEs*

The site PI is responsible for evaluating SAEs submitted by the study pediatrician within 24 hours to convene a safety review if the investigator reported the SAE as fatal or life-threatening and suspected to be related to study drug. Medical officer(s) from PATH serving as technical consultants will provide technical guidance regarding SAE management including classification and reporting.

### *Sponsor Reporting to Regulatory Agency*

The sponsor has authorized the site PI to execute its responsibility for safety reporting to the appropriate regulatory authorities within specified time period of notification.

The site PI will be responsible for reporting to the Kenya MOH PPB, in accordance with applicable regulatory requirements.

- All fatal and life-threatening, unexpected adverse study product reactions (i.e., SUSARs) should be reported within 7 calendar days after first knowledge by the applicant. The initial notification must be followed by as complete a report as possible, within an additional 8 calendar days.
- SUSARs that are not fatal or life-threatening must be reported as soon as possible and not later than 15 calendar days after first knowledge by the applicant.
- PPB must be notified, within 15 calendar days after first knowledge by the applicant, when there is a suggestion of a change in the nature, severity, or frequency of expected adverse drug reactions or when new risk factors are identified. The basis on which these assessments are made should be included.
- Any information that may in any way influence the benefit-risk assessment of a medicine or that would be sufficient to consider changes in the administration of the medicine or in the overall conduct of a clinical trial must be reported to PPB.

- A safety report will be submitted to PPB once a year throughout the clinical trial, or on request by PPB, that takes into account all new available safety information received during the reporting period. The aim of the annual safety report is to describe concisely all new safety information relevant for the clinical trial and to assess the safety conditions of subjects enrolled. The safety report shall include a summary of all SAEs and SUSARs.

#### *Safety Oversight*

The site PI and designated study staff will be responsible for safety monitoring of all study participants and for alerting the PI if unexpected concerns arise. This study will also have a Data and Safety Monitoring Board (DSMB), composed of two pediatric gastroenterologists (one as chair) and a biostatistician. The DSMB is responsible for safeguarding the interests of study participants, assessing the safety of study procedures, and for monitoring the overall conduct of the study. The DSMB is an independent group advisory to the study investigators. The responsibilities are outlined in detail in the DSMB Charter, which will be approved by the DSMB prior to the study's start.

DSMB meetings will be held remotely. The purpose of the first meeting held before the study begins recruitment is to review and discuss the Charter, to review the protocol and informed consent form, and to confirm the report contents and format for data reports during interim and final DSMB meetings. Enrollment in the study will not begin until the DSMB's Charter has been accepted by the DSMB and IRB/regulatory approval has been obtained. The DSMB is expected to meet twice more over the course of the study. One meeting will be held to review interim data when approximately half of the participants have been enrolled or two months have elapsed after the beginning of recruitment, whichever is earlier. The final meeting will be held at the end of data collection, once topline data is available. Additional meetings or conference calls will be scheduled as needed. At the interim meeting, the DSMB will also review formal interim analyses of the primary (safety) endpoint.

There are no *a priori* reasons for a particular safety concern or the possibility of serious toxicity with the study product. As a small, single-site study for a short duration, the trial pediatrician will be able to have close supervision and monitoring of all AEs. Additionally, an ISM will be contracted to oversee compliance with safety monitoring and stopping rules (e.g., weight loss  $\geq$  5%, cessation of breastfeeding by 2 of the first 10 breastfeeding participants).

#### xi. Data management and analysis plan

##### *Data Management Procedures*

IDI data will be analyzed qualitatively, using transcripts and notes to identify key themes and topics.

DOs will be manually coded and analyzed to identify the time taken to drink up to 237 ml of AA-ORS, ease of administration, and visible signs of palatability.

Quantitative clinical data focused on demographics, anthropometrics, AEs, product volume consumed daily, plasma/serum micronutrients, metabolic markers (acylcarnitine profile), EED markers (gut dysfunction and growth hormone resistance), and systemic inflammation will be collected on standardized forms or exported to computerized databases by RAs and laboratory workers. Form data will be double entered into a password-protected Microsoft Access database by RAs blinded to the supplementation assignment (AA-ORS vs. placebo). After entering all data and resolving inconsistencies, the data set will be locked.

All data will be stored on password-protected computers in PATH offices. Only members of the study team will have access to the raw transcripts, CRFs, and consent forms in a locked filing cabinet.

*Data Analysis Procedures***DEFINITIONS OF POPULATIONS TO BE ANALYZED**

**The intention-to-treat population** will include all participants who are assigned AA-ORS or placebo regimen and receive at least one dose, regardless of whether he/she completes the full 14-day regimen (or misses dose[s] of study product for a medical reason such as vomiting). The first primary (safety), secondary (caregiver acceptability), and exploratory (biomarker) analyses will be performed using this population.

**The per-protocol population** will include all participants who are assigned a regimen with no major protocol violations that are determined to potentially interfere with the ad-libitum dosing of the study solution(s) (i.e., early withdrawal or product discontinuation, etc.). This population will serve as the primary analysis population for the volume consumption and consumption factor endpoint. As the primary objective is to accurately estimate the average daily volume consumed in the full sample (AA-ORS + placebo), it is critical that all subjects in the population have completed a full dosing regimen.

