## STUDY OVERVIEW

Title:	Safety, Acceptability, and Feasibility of enterade® in children at risk for environmental enteric dysfunction in Kakamega County, Kenya
Sponsor:	Drug Development, PATH
Investigators:	USA: [name] (co-PI), [name], [name] Kenya: [name] (co-PI), [name], [name]
Ethics committees:	Maseno University Ethics and Research Committee (MUERC) PATH Research and Ethics Committee (REC)
Regulatory authority:	Kenyan Ministry of Health (MOH) Pharmacy and Poisons Board (PPB)
Phase:	I
Study goals:	Determine the safety, acceptability, and pediatric dosing of enterade® solution, an amino acid–based oral rehydration solution (AA-ORS), for potential use in the management of environmental enteric dysfunction (EED) among children aged 12–24 months in Kenya.
Study objectives:	
 
1. Primary: To determine the safety of a 2-week course of AA-ORS among children with length-for-age Z-scores (LAZ) between –1 and –3.
 
2. Primary: To determine the feasibility and best tolerated dose of AA-ORS among children with LAZ between –3 and –1.
 
3. Secondary: To determine the perceptions among caregivers on the acceptability of AA-ORS as a potential intervention for EED.
 
4. Exploratory: To determine the impact of AA-ORS on markers of metabolism, gut dysfunction, systemic inflammation, and micronutrient status among children with LAZ between –3 and –1.
 

Study endpoints:	
 
1. Primary: Adverse events and serious adverse events through 21 days of follow-up, and changes to dietary and digestive habits through day 14 of follow-up.
 
2. Primary: Average daily product volume consumed through 14 days of follow-up, time trends in average daily volume consumed, and factors that influence children’s willingness and ability to ingest the product as intended.
 
3. Secondary: Key factors that influence caregivers’ willingness to have the product used by their children, and their perception of their children’s response to its consumption.
 
4. Exploratory: Average plasma/serum concentrations of metabolic, gut dysfunction, systemic inflammation, and micronutrient biomarkers at baseline and day 15 of follow-up.
 

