#### Objectives

**PRIMARY OBJECTIVE:** To determine the safety of AA-ORS among children with mild to moderate stunting, administered as a daily dose over 2 weeks, ad libitum up to 237 ml in 3 hours.

*Safety assessment in children will compare adverse event (AE) and serious adverse event (SAE) rates and changes to dietary and digestive habits between children receiving AA-ORS versus an inactive placebo solution containing no amino acids.*

**PRIMARY OBJECTIVE:** To determine the feasibility and well-tolerated dose of AA-ORS among children with mild to moderate growth stunting administered as a daily dose over 2 weeks, ad libitum up to 237 ml in 3 hours.

*User preferences among children include average daily volume consumed over 14 days, trends in volume consumed, and factors that influence children's willingness and ability to ingest the product as intended.*

**SECONDARY OBJECTIVE:** To determine the perceptions among caregivers on the use and acceptability of this product as a potential intervention for EED.

*Acceptability by caregivers includes factors that influence their willingness to have the product used by their children and their perception of their child's response to its consumption.*

**EXPLORATORY OBJECTIVE:** To determine the impact of AA-ORS on gut dysfunction, metabolism, gut and systemic inflammation, and micronutrient status.

*Impact of AA-ORS on gut dysfunction, systemic inflammation, and micronutrient status will be assessed by comparing non-invasive biomarker levels in blood samples collected following the intervention. These biomarkers will be assessed in both groups at baseline in order to have setting-specific descriptive data with which to power a future EED efficacy trial.*

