The study will be double-blinded as both study staff and participants will be blinded to study product allocation. Active and control product bottles will be labeled with identical product information. Each bottle will be also labeled with a randomization number assigned to a particular participant according to the appropriate allocation arm. The randomization list where randomization number and allocation code are provided will be maintained in a secure place by an independent statistician. The participants

will thus be blinded to whether they receive AA-ORS or the control solution. Study staff administering the study product and laboratory staff performing any laboratory testing will also be blinded to the product allocation.

This study will provide critical information about the safety of AA-ORS in this at-risk pediatric population and qualitative and quantitative information on the user-preferred product volume for this age group, palatability, and ease of administration. The study will also describe whether the product can be feasibly consumed for a 2-week period and if there are differences in gut health between AA-ORS and placebo groups based upon diarrhea frequency and plasma biomarkers of systemic inflammation and gut damage/repair at the end of follow-up. However, the study has not been statistically powered or designed to answer such gut health questions. Even though such exploratory comparisons will be underpowered, the baseline and follow-up biomarker data will be useful for informing study design and sample size of future EED clinical trials in this setting.

The questionnaire guides are a mix of structured and semi-structured questions. Structured questions are necessary to standardize responses to questions such as the experience with diarrheal disease treatment. Semi-structured questions allow for flexibility and richness in responses, especially those on perceptions and experiences around AA-ORS use and acceptability. Semi-structured questions are open-ended and allow for probing a participant's answers for in-depth responses. The DO checklist includes a list of questions to assess the administration of AA-ORS and explore ease of use, palatability, and acceptance of the product by the user(s).

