**STUDY ENDPOINTS TO BE ANALYZED AND ANALYTICAL METHODOLOGY**

**Primary:** AEs and SAEs through 21 days of follow-up, and changes to dietary and digestive habits through day 14 of follow-up.

*For AEs and SAEs that occur within 21 days of enrollment, statistical comparisons will be made between the AA-ORS and the placebo solution groups using Fisher's exact test. Changes to feeding habits (normal, less frequent/less volume, more frequent/more volume), diarrhea (1–2, 3–4, 5–7, or 7+ events in 24 hours), and vomiting (none, 1, 2–5, > 6 events in 24 hours, or hospitalization) will be made using chi-square tests.*

**Primary:** Average daily product volume consumed through 14 days of follow-up, time trends in daily volume consumed, and factors that influence children's willingness and ability to ingest the product as intended.

*The average daily volume (and statistical distribution) of solution consumed by children over the 2-week period will be calculated. These descriptive data will be pooled from AA-ORS and placebo arms as the solutions are designed to taste the same. Lowess curves will be used to describe trends in volumes consumed, and linear mixed effects models will be used to test for an association between day of follow-up and product volume consumed. We will use linear regression to identify factors (e.g., child weight, length, and age) associated with a child's average daily intake.*

**Secondary:** Key factors that influence caregivers' willingness to have the product used by their children, and their perception of their children's response to its consumption.

*These qualitative analyses will use ATLAS.ti software to identify and group key themes and topics from IDI notes.*

**Exploratory:** Average plasma/serum concentrations of metabolic, gut dysfunction, systemic inflammation, and micronutrient biomarkers at baseline and day 15 of follow-up.

*Metabolic, EED, systemic inflammation, and micronutrient marker data collected at baseline will be pooled across intervention groups and used to generate descriptive statistics for the study population. The same descriptive statistics will be generated for day 15 of follow-up. Paired student's t test will be used to compare these continuous parameters between baseline and day 15 of follow-up.*

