Volume of solution too great.	237 ml may be too much volume for children.	Children to drink as much or as little of the solution (up to 237 ml) as desired over 3 hours. Gavage will not be done. Breastmilk will be permitted throughout this period.	Need to measure and calculate the average daily volume consumed during follow-up in order to guide dosing recommendations in future clinical trial.
Blood draw in children.	Potential discomfort, bleeding, bruising, and minimal risk of infection.	Precautions will be taken to avoid introduction of infection by disinfecting the site of venipuncture and using sterile equipment. The risk of bleeding and bruising will be minimized by immediate application of pressure after venipuncture.  Only trained, experienced phlebotomist will perform venipunctures.	Blood samples are needed in order to measure metabolic profile and biomarkers of gut dysfunction, systemic inflammation, and micronutrient status.  Metabolic profile assessment will be an important part of exploratory analysis; it is helpful to determine if the absence of certain essential amino acids leads to increase in oxidative pathways.  These biomarker measurements are important in order to have setting-specific descriptive data with which to power a future EED efficacy trial.  A comparison of these non-invasive biomarkers following the intervention will also be done.
Loss of confidentiality.	Medical information from a participant's medical record or other	Access to study records will be limited to study staff with electronic passwords (data files) or	Review of medical records will help ensure that only eligible

Potential risk to participant	Concern	Study design feature intended to minimize risk	Rationale for the necessity of exposing participants to risk
	study documents are shared inappropriately.	lock and key (physical records).  Study staff will only review medical records for eligibility assessment and will not make copies or remove such records from the hospital premises.  If the caregiver declines enrollment in the study, any medical record data collected will be discarded.	participants are enrolled in the study.  Detailed study records are critical for data analysis and reporting results accurately.

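### Volume, the second primary endpoint, is planned mainly in children who complete the regimen and is pooled with placebo; no AA-ORS volume and no volume in all dosed children is specified

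*Combined protocol and SAP*

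**What the plan says.** The objective is written for AA-ORS alone. The Study Overview has "To determine the feasibility and best tolerated dose of AA-ORS", and C.ii Objectives has "To determine the feasibility and well-tolerated dose of AA-ORS among children with mild to moderate growth stunting". Section C.iii adds a purpose: "The study will also describe whether the product can be feasibly consumed for a 2-week period". Table 7 in section D.i says what the volume figure is for: "Need to measure and calculate the average daily volume consumed during follow-up in order to guide dosing recommendations in future clinical trial".

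Section C.xi, under the definitions of populations, sets up two analysis sets. The intention-to-treat (ITT) set holds every child who is assigned a regimen and takes at least one dose. It is used for safety, caregiver acceptability and biomarkers. The per-protocol set leaves out children with major violations, and gives early withdrawal and stopping the product as instances. Of the per-protocol set it says "This population will serve as the primary analysis population for the volume consumption and consumption factor endpoint". The reason given is that "it is critical that all subjects in the population have completed a full dosing regimen", and the target is described as average volume over both arms together.

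Under the endpoint methods in C.xi: "These descriptive data will be pooled from AA-ORS and placebo arms as the solutions are designed to taste the same". A mixed model tests volume against day, and a regression looks for factors such as weight, length and age. Arm is named in neither. For adverse events, by contrast, "statistical comparisons will be made between the AA-ORS and the placebo solution groups".

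Two further provisions bear on this. The section on discontinuation and withdrawal in C.iii lists noncompliance with the regimen and adverse events among the reasons for taking a child off product. It also says in general terms that data gathered before a withdrawal will be analysed, without naming an endpoint or a population. The missing-data paragraph in C.xi plans a check for differential missingness by arm on the primary endpoints, and no imputation.

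**The concern.** In an ad libitum study, completing 14 days is itself an outcome of how well the product is taken. Low intake alone does not remove a child from the per-protocol set, but being stopped for noncompliance or an adverse event does. A mean over completers can therefore leave out the children who managed the product least well. This is the figure meant to inform dosing in a later trial.

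Pooling raises a second question. The placebo lacks the amino acids (sections C.i and C.iv), and equal taste is a design intention. If intake differs between arms, the pooled mean is not the AA-ORS mean, and no planned volume summary would show it.

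**Working it through.** **1. The plan's own figure.** The only design calculation for a primary endpoint is the chance of seeing at least one adverse event with 30 children at a 10% rate: 1 − 0.9^30 = 0.958, as in Table 6. It reproduces. The documents give no mean, SD or precision target for volume, so every volume figure below rests on stated assumptions.

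**2. Completers against all dosed children.** Let q be the fraction of dosed children left out of the per-protocol set, and f their mean intake per observed day relative to completers. With each child's daily mean weighted equally:

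- all-dosed mean ÷ completers' mean = (1 − q) + q·f
- overstatement = 1/[(1 − q) + q·f] − 1
- most it can be in ml/day = 237·q·(1 − f), because completers cannot average more than 237 ml

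The documents give no per-protocol exclusion rate. I borrow q = 0.10 from the dropout cap in the Sampling Strategy, which concerns a different event. The values of f are assumptions.

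| f | ratio at q = 0.10 | overstatement | most, ml/day |
|---|---|---|---|
| 1 | 1.000 | 0% | 0 |
| 0.75 | 0.975 | 2.6% | 5.9 |
| 0.5 | 0.950 | 5.3% | 11.9 |

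With 6 of 66 children left out (q = 0.091), the overstatement is 0%, 2.3% and 4.8%, or at most 0, 5.4 and 10.8 ml/day.

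The weighting matters. If days rather than children count equally and excluded children stop after 7 days, the ratio is (14(1 − q) + 7·q·f)/(14(1 − q) + 7·q). At q = 0.10 and f = 0.5 it is 12.95/13.3 = 0.974, an overstatement of 2.7%. At f = 0.75 it is 1.3%.

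**3. Pooling.** With equal arms, and placebo intake exceeding AA-ORS intake by D ml/day, the pooled mean minus the AA-ORS mean is D/2. The sign follows D. The documents give no D. As an illustration only, D of 0 to 30 ml gives 0 to 15 ml.

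**4. Precision of what could be added.** Assume an SD of 60 ml. The 95% half-width for a mean is t·SD/√n: 21.3 ml for one arm (n = 33) and 14.7 ml pooled (n = 66). For the arm difference it is t·SD·√(2/33) = 29.5 ml, and 19.7 to 39.3 ml for SDs of 40 to 80 ml.

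**5. When pooling is the better estimator.** The pooled mean has the smaller mean squared error for AA-ORS intake when SD²/66 + (D/2)² < SD²/33, that is when D < 2·SD/√66. At SD 60 ml this is 14.8 ml.

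**The case against.** Much of the other side stands.

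- **The text does not rule out an all-dosed analysis.** C.xi calls the per-protocol set primary, not sole, and the withdrawal section promises some use of pre-withdrawal data. A reader might infer that these children's volumes are discarded. The documents do not say so. They also do not place those data in the volume analysis, so the two passages need reconciling.
- **Pooling is deliberate.** Section C.iv explains that placebo children also inform the feasible dose, and C.xi states a two-arm target. A reader might infer a contradiction from the reference to the full sample. There is none: it means both arms. By step 5, pooling is also the more accurate choice when the arm difference is small. And the regression factors are given as examples, so arm is not excluded.
- **Tolerability is not ignored.** Adverse events, feeding and vomiting are tested, and differential missingness is checked by arm. The lack of a listed completion proportion is therefore largely a reporting preference.
- **The bias is modest.** The completer effect in step 2 is below the pooled half-width of about 15 ml at the assumed SD.
- **A mean of per-child means has a weakness.** A child who stops after the supervised first dose counts as much as one with 14 days.

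What remains is that none of these provisions produces a volume by arm or a volume in all dosed children.

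**Conclusion.** The point holds as a gap in a primary analysis that is cheap to close. The objective concerns AA-ORS, yet the specified volume figure is a two-arm mean in children who finished. Its distance from AA-ORS intake in all dosed children is unknown from the documents. Under the assumed 10% exclusion and intake of 50% to 100% of completers' per observed day, the completer effect is 0% to about 5%, at most about 12 ml/day. Pooling adds or subtracts half of any arm difference, and nothing if intake is equal.

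A reader might infer a much larger error by counting days after stopping as zero intake. With 6 of 66 lost this gives 66/60 = 1.10, or 10%. With all 6 in the AA-ORS arm it gives 33/27 = 1.22, or 22%. That is a different quantity from intake on days when product was offered, and the documents support neither the zero intake nor the one-sided loss.

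**What to change.** In C.xi:

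- Add a volume summary in the existing ITT set, using all observed days and no imputation, beside the per-protocol one. State the weighting (child or day) and the number of days each child contributes.
- Say there whether the withdrawal section's promise covers volume, so that the two sections agree.
- Let the mixed model use all observed days.
- Report the mean and distribution of volume by arm, with the arm difference and its 95% CI, beside the pooled figure. Add arm to the mixed model and to the regression.

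Two changes are optional: making the ITT set primary for volume, and reporting the proportion completing 14 days by arm.

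No new data are needed. Residual solution is already measured for each bottle (C.x, Safety Monitoring), and bottles carry the randomization number (C.iii). The cost is a protocol amendment, since the analysis plan is part of the protocol and section A requires sponsor agreement and documented ethics and regulatory approval. By-arm means will be less precise than the pooled one (about ±21 against ±15 ml at the assumed SD of 60 ml). The arm difference, at about ±30 ml, is descriptive and cannot prove equal intake.
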